The phase II coopERA trial (NCT04436744) was a two arm, open-label, multicenter trial aimed at evaluating the efficacy, safety and pharmacokinetics of giredestrant (GDC-9545) plus palbociclib compared with anastrozole plus palbociclib in postmenopausal women with untreated ER-positive/HER2-negative EBC. 221 patients with baseline Ki67 score $\geq 5\%$ were randomized 1:1 to receive 14 days of anastrozole (1 mg, PO QD) or giredestrant (GDC-9545) (30 mg, PO QD) (window-of-opportunity phase, WoO) followed by 16 weeks (four 28-days cycles) of additional neoadjuvant palbociclib (125 mg, PO, D1-21) treatment prior to surgery. The primary objective of the study was to measure tumoral Ki67 changed between baseline and post-WoO samples. In ESMO Breast 2021, preliminary results were shown for 83/202 planned patients. Two-week relative Ki67 reduction was significantly greater with giredestrant (GDC-9545) than anastrozole (80% versus 67%, respectively) and a consistent Ki67 suppression was observed in patients with baseline Ki67 $\geq 20\%$ (giredestrant (GDC-9545): 83% reduction; anastrozole: 71%) or $< 20\%$ (65% vs 24%). After 14 days of treatment, 25% of tumors exhibited complete cell cycle arrest (secondary objective) with giredestrant (GDC-9545) versus 5% with anastrozole. Patients treated with giredestrant (GDC-9545) had fewer AEs than anastrozole.

Table 2 summarizes ongoing clinical trials with giredestrant (GDC-9545) for the treatment of early or advanced hormonal receptor-positive BC. In addition, giredestrant (GDC-9545) is also being studied in the treatment of ER-positive/HER2-positive BC.

Table 2. Ongoing clinical trials with giredestrant (GDC-9545) in BC.

Clinical Trial	Phase	Study
NCT03916744	I	A Phase I, Multicenter, Open-Label Preoperative, Short-Term Window Study of GDC-9545 in Postmenopausal Women With Stage I-III Operable, Estrogen Receptor-Positive Breast Cancer
NCT03332797	Ib/II	Multicenter, Open-Label, Dose Escalation, Dose Expansion Study Evaluating the Safety, Pharmacokinetics, and Activity of GDC-9545 Alone or in Combination With Palbociclib and/or LHRH Agonist in Patients With Locally Advanced or Metastatic Estrogen Receptor-Positive Breast Cancer
NCT04802759	Ib/II	Open-Label, Multicenter, Randomized Umbrella Study Evaluating the Efficacy and Safety of Multiple Treatment Combinations in Patients With Breast Cancer (MORPHEUS-Breast Cancer)

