1.6 Sample Size

The analysis will compare absolute changes for Ki67 expression between baseline score and the evaluation after the treatment. The sample size was based on a superiority contrast between two study arms analyzed with a two-sided t-test set at 0.05 alpha level. We assumed a 70% mean in giredestrant (GDC-9545) Arm vs. 50% mean in tamoxifen

with a 29% common standard deviation, according to the results observed (Dowsett, Smith, et al., 2005). We planned 34 patients per arm to attain an 80% power.

The final analysis will be conducted with unpaired Wilcoxon test because of the non-asymptotic distribution of data. We assumed that asymptotic efficiency of Wilcoxon test relative to the t-test, never falls below 0.86 (Jr & Lehmann, 1956). In addition, we expect a 10% dropout rate. So, 46 patients per arm will be finally recruited. We used the R software version 4.0.2. released on 2020-06-22 ("pwr").

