2.4 Endpoints definitions

Primary endpoint:

Changes in tumor cell proliferation as measured by Ki67 expression between baseline and post-treatment tumor biopsy samples by central assessment in patients with centrally confirmed Ki67 $\geq 10\%$ (Arm A vs Arm B).

Secondary endpoints:

- CCCA in all arms, defined as the percentage of participants with centrally assessed Ki67 scores $\leq 2.7\%$ stained nuclei upon treatment (post-treatment sample).
- Changes in markers (such as ER and PgR levels) and molecular profiling using HTG (PAM-like molecular test).
- Incidence and severity of adverse events (AEs), with severity determined in accordance with NCI-CTCAE v.5.0.

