4.4.2 Secondary Endpoints and Subgroup Analysis

The secondary efficacy endpoints will be done for the mITT analysis set. We only will analyze observed valid cases.

For quantitative measures (Ki67, ER, PR, and other molecular markers) the mean, median, geometric mean, standard deviation, interquartile range, and range will be reported as appropriate per study arm and visit. Summary statistics for the absolute and relative change between baseline and post-treatment will be also reported.

Individual baseline and post-treatment scores in quantitative measures will be summarized with dot plots linking with a line the observations of the same patient. Absolute and relative change between baseline and post-treatment will be summarized with waterfall and bar plots.

The difference between baseline and post-treatment evaluation will be compared in each arm with Wilcoxon paired test. We will estimate the 95% confidence intervals (CI) for the mean and median.

The difference between study arms at baseline and after the treatment will be compared with Wilcoxon unpaired test. We will estimate the 95% confidence intervals (CI) for the mean and median difference between treatments with T-Test and Hodges–Lehmann estimator, respectively. The comparison of quantitative score after two weeks of treatment in each arm will be adjusted by baseline scores based on linear regression.

For qualitative measures (CCCA [Ki67 \leq 2.7%] after the treatment) we will calculate the number and proportion of patient achieving the cut-off criterion. We will estimate the proportions with the 95% Clopper-Pearson confidence intervals. The between arms comparison will be conducted with logistic regression models. Factor estimates, odds ratios, corresponding 95% confidence intervals, and p-value will be presented. P-values and 95% confidence intervals will be based on Wald test.

The comparison of primary and secondary endpoints between patient and molecular characteristics will be conducted if considered appropriate. The quantitative endpoints will be analyzed with linear regression based on Wald test. The binary endpoints will be analyzed with logistic regression models. Factor estimates, odds ratios, corresponding 95% confidence intervals, and p-value for applicable test statistics will be presented. P-values and 95% confidence intervals will be based on Wald test.

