For all secondary analyses, we will use two-sided p-values with $\alpha \leq 0.05$ level of significance and 95% confidence intervals.

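### No baseline Ki67 covariate is specified for the between-arm comparison of complete cell cycle arrest (CCCA), so a small and cheap gain in precision goes unused

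*SAP*

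**What the plan says.** SAP 2.4 defines CCCA by the post-treatment central Ki67 score alone; the starting value plays no part. SAP 4.4.2 sets the population ("The secondary efficacy endpoints will be done for the mITT analysis set") and uses observed cases. For the comparison of arms it says "The between arms comparison will be conducted with logistic regression models", followed by "P-values and 95% confidence intervals will be based on Wald test". Protocol 8.7 has the same text. Neither names a covariate, and neither says that the model is unadjusted. The significance level is two-sided 0.05.

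The same SAP section treats continuous markers differently: "The comparison of quantitative score after two weeks of treatment in each arm will be adjusted by baseline scores based on linear regression". Rows 4 to 6 of SAP Table 1 also model post-treatment Ki67 with baseline Ki67 as covariate. A later paragraph of SAP 4.4.2 allows optional models of endpoints by patient and molecular characteristics, but does not say that these adjust the treatment contrast.

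Protocol 6.1.2 describes 1:1 allocation from a schedule and mentions no stratification factor. SAP 3 requires a central baseline Ki67 of at least 10% for the mITT set, so the covariate is complete there.

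**The concern.** CCCA is the post-treatment Ki67 score cut at a fixed value. It is the one form of that score for which the plan does not specify the baseline term it uses elsewhere, and no reason is given. If tumours with lower baseline Ki67 reach 2.7% more easily, an arm that happens to hold more of them will show more CCCA for reasons unrelated to the drug. Nothing in the described randomisation prevents such an imbalance, and a predictor already in the database would go unused.

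The silence also matters in itself. In an open-label trial, a logistic model with unstated covariates leaves a choice that could be made after the results are seen.

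**Working it through.** **1. The plan's own sample size.** SAP 1.6 assumes means of 70% and 50%, an SD of 29% and 80% power, "analyzed with a two-sided t-test set at 0.05 alpha level". The normal approximation gives 2 × (1.96 + 0.84)² × 29² / 20² ≈ 33.0, just above 33, so 34 per arm. The noncentral-t calculation gives 33.99, also 34. Then 34/0.86 = 39.5, rounded to 40, and 40/0.9 = 44.4, rounded to 45, within one of the stated 46. With 10% dropout, 46 × 0.9 = 41.4, so about 41 evaluable per arm. Other mITT exclusions would lower this. No power is stated for CCCA.

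**2. Fall needed to reach 2.7%** = 1 − 2.7/baseline:

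| Baseline Ki67 | 10 | 15 | 20 | 30 | 40 |
|---|---|---|---|---|---|
| Fall needed | 73% | 82% | 86.5% | 91% | 93% |

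This makes CCCA harder at high baseline only if the relative fall does not itself grow with baseline.

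**3. What the documents report about that.** Protocol 1.5.1 cites an earlier randomised giredestrant trial in postmenopausal patients. At baseline Ki67 of 20% or more it gives "giredestrant (GDC-9545): 83% reduction; anastrozole: 71" per cent; below 20% the figures are 65% and 24%. So relative falls were larger at higher baseline. With illustrative baselines (assumed, not in the documents), giredestrant gives:
- 15 × 0.35 = 5.25 and 30 × 0.17 = 5.1, almost no gradient;
- 10 × 0.35 = 3.5 against the same 5.1, a log-log slope of ln(5.1/3.5)/ln(30/10) ≈ 0.3.

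Taking those reductions as geometric means within each band, with the baseline distribution of step 4 and a residual log-SD of 0.9, giredestrant CCCA is about 23% below 20% and 24.5% at or above it. At log-SD 0.6 the pair is 14% and 16%; at 1.2 it is 29% and 30%. Some dependence within bands remains (correlation of CCCA with log baseline about −0.1).

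**4. Simulated power, 41 per arm.** Assumptions not in the documents: baseline lognormal with median 22% and log-SD 0.5, truncated to 10–100%; log post-treatment Ki67 linear in log baseline with the slope shown; residual log-SD 0.9 or 0.6. CCCA rates are set at 51% vs 25% or 25% vs 5%. Protocol 1.5.1 gives 51% for giredestrant in a phase I study, and 25% vs 5% against anastrozole; the 25% control rate is assumed. Each cell is the Wald logistic test, arm only → arm plus log baseline.

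| Slope | 51 vs 25, SD 0.9 | 51 vs 25, SD 0.6 | 25 vs 5, SD 0.9 | 25 vs 5, SD 0.6 |
|---|---|---|---|---|
| 0 | 70→69 | 69→68 | 59→59 | 58→59 |
| 0.5 | 71→71 | 69→71 | 58→60 | 56→59 |
| 1 | 70→74 | 70→78 | 57→61 | 57→65 |
| 1.5 | 69→78 | 70→86 | 58→66 | 57→70 |

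Slope 1 means post-treatment Ki67 proportional to baseline. The unadjusted test rejects in 3.6–4.3% of null trials.

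**5. Chance imbalance.** The between-arm difference in mean log baseline has an SD of about 0.1. The shift in the unadjusted odds ratio per SD is exp(|c| × SD), where c is the simulated dependence of the log odds ratio on that difference. At slope 1, 51% vs 25% and residual SD 0.9, exp(1.71 × 0.099) = 1.18. Across settings the factor is 1.01 at slope 0, 1.10–1.14 at slope 0.5, 1.16–1.24 at slope 1 and 1.20–1.32 at slope 1.5. In the worked case the shift is 0.17 on the log scale against a standard error of 0.48, about a third of it. Adjustment removes most of the shift.

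**6. Few events.** At 25% vs 5%, expected events are 41 × 0.25 + 41 × 0.05 ≈ 12, about 2 of them in the control arm. The chance of none there is 0.95^41 ≈ 12%. Power is 73% by a two-proportion formula but about 58% for the planned Wald test.

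**The case against.** The strongest reply is that the plan is adequate as it stands. Randomisation makes the unadjusted comparison valid, and its confidence interval already allows for chance imbalance. Crude proportions are a legitimate marginal estimand. CCCA is secondary, unpowered and outside the superiority rule in SAP 4.4.1, and SAP 4.1 calls the study exploratory. The continuous score that CCCA dichotomises carries more information and is already adjusted in SAP Table 1. A further model term is not free when about 12 events are expected.

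All of this stands, and it limits the point to a matter of efficiency and clarity. It does not justify leaving the covariate unstated. If baseline is irrelevant, including it costs about one power point at most in step 4; if it is predictive, there is a gain.

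A reader might infer more from the arithmetic in step 2: that CCCA depends strongly on baseline, or that the planned comparison is biased. The documents support neither. Step 2 assumes that relative fall is unrelated to baseline, and protocol 1.5.1 reports the opposite pattern. Those data are preliminary, postmenopausal and from a trial that enrolled at Ki67 of 5% or more, so they do not show that dependence is absent either. Chance imbalance adds variance, not systematic bias. Nor does the SAP say that the model is unadjusted; it is silent.

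**Conclusion.** The point holds as a cheap improvement. The plan specifies no baseline term for CCCA, although the covariate is complete in the mITT set and is used for the underlying score. The power change is about nil (−1 to +3 points) at slopes of 0 to 0.5 and a gain of 4 to 8 points at slope 1. The 8 to 16 points at slope 1.5 need a dependence that nothing in the documents suggests. These sizes rest on the assumed baseline distribution, residual spread and CCCA rates, and on 41 evaluable per arm. The slope in premenopausal patients is unknown; the cited results suggest it may be modest. Severity is low and confidence medium.

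**What to change.** In SAP 4.4.2 and protocol 8.7, state that the CCCA model contains arm and log central baseline Ki67 as a continuous covariate, fitted by penalised (Firth) or likelihood-based logistic regression instead of Wald inference, because few events are expected. Report the baseline-standardised difference in CCCA proportions with its 95% CI as the treatment effect. Keep the crude proportions with Clopper-Pearson intervals alongside.

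The cost is a sentence or two in each document and no new data. There are two small downsides. The model carries a second term on few events. The adjusted odds ratio is also a different estimand from the crude one: at slope 1 with 51% vs 25%, the median is about 3.9–4.5 adjusted against 3.3 crude. Naming the standardised difference as the reported effect avoids that ambiguity.

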4.5 Safety analysis

Safety data will be analyzed in safety analysis set. All safety measures will be described in each arm. We will summarize adverse events and adverse events (AE) of special interest (AESI), premature withdrawal from study medication, laboratory parameters, exposure to study medication, concomitant medications, vital signs, ECOG performance status, and physical examination.

The number and percentage of AEs and SAEs will be summarized according to the primary system-organ class (SOC) and within each SOC, by the Medical Dictionary for Regulatory Activities (MedDRA) preferred term (PT). Additional summaries by frequency tables will also be provided for the AEs. Patients who died will be listed together with the cause of death.

Laboratory parameters, hematology and biochemistry, will be presented in shift tables of NCI-CTCAE grade at baseline versus worst grade during treatment.

Other safety variables, such as exposure to study medication, ECOG performance status, concomitant medications, vital signs, and physical examination, will be analyzed in a similar way. Frequency tables will summarize the exposure of study medication.

4.5.1 Drug administration

The drug administration endpoints are:

- Duration of treatment (months):

$$\frac{(\text{date of last medication}) - (\text{date of first medication administration}) + 1}{30.25}$$
, when the date of last medication is known and complete.
- Duration of follow-up (months): $\frac{(\text{date of last visit}) - (\text{date of baseline}) + 1}{30.25}$, where last visit date could be the last day of follow-up, or date of death, or date of last visit before a dropout.
- Relative Dose intensity: $\frac{\text{Cumulative dosage received (mg/Kg)}}{\text{Product of the assigned dose (mg/kg)}}$, based on the number of doses the patient was scheduled to receive during the patient's treatment period.
- Dose reduction: Patients with at least a dose reduction in the study.
- Dose delay: Patients with at least a dose delay in the study.
- Discontinued patients: Patients who discontinued the study.

These parameters will be summarized using measures of central tendency and dispersion; mean, median, standard deviation, 25% and 75% percentiles (Q1 and Q3) and extreme values (minimum and maximum).

4.5.2 Adverse Events

The adverse events will be tabulated per arm containing the number and percentage of subjects with the following:

- Subjects with at least one Adverse Event; and number of reported adverse events
- Subjects with at least one AE of special interest (AESI); and number of AESI
- Subjects with at least one Serious Adverse Events (SAEs); and number of SAEs
- Subjects with at least one AE related to the treatment; and number of AE related to the treatment
- Subjects with at least one SAE related to the treatment; and number of SAE related to the treatment

- Subjects who died due to SAEs; and number of SAEs that caused death
- Subjects that dropout due to SAEs; and number of SAEs that caused discontinuation
- Subjects with at least one treatment-emergent adverse event (TEAE); and number of reported TEAE. Adverse events starting or worsening during treatment phase will be considered as TEAEs.
- Subjects with at least one TEAE Grade ≥ 3 ; and number of reported TEAE Grade ≥ 3 .

The AEs will be also summarized according to the primary SOC and within each SOC, by PT according to the Medical Dictionary for Regulatory Activities (MedDRA). The duration of AE will be calculated as follows:

- Duration of an AE (days): (*date of resolution*) – (*start date*) + 1 when both end and start dates of AE are known and complete.

Missing data imputation methods

When data is not completed it will be considered as:

- Day 15 if day is missing
- Day 1 and month July if day and month are missing

In the event of not being able to allocate an AE, it will be considered as being a TEAE. Any missing information will be considered as being the worst case scenario (serious and treatment related).

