9. **AE reporting:** After informed consent has been obtained but prior to initiation of study drug, only serious adverse events caused by a protocol-mandated intervention should be reported with grading according to the NCI–CTCAE v.5.0 criteria. After initiation of study drug, all adverse events will be reported until 28 days (EoS) after the final dose of study treatment. After this period, the Sponsor should be notified if the investigator becomes aware of any serious adverse event that is believed to be related to prior study drug treatment.
10. **Concomitant medication reporting:** Medication (e.g., prescription drugs, over-the-counter drugs, vaccines, herbal or homeopathic remedies, nutritional supplements) used by a patient in addition to protocol-mandated treatment from 14 days prior to initiation of study drug until end of study visit.
11. **12-lead ECG:** Patients should be resting in a supine position for at least 10 minutes prior to ECG recording. All ECGs will be obtained prior to other procedures scheduled at that same time (e.g., vital sign measurements, blood draws). All patients must have a standard 12-lead ECG in screening period, maximum 48h before start of treatment dose, in the EoT visit and in the EoS visit.
12. **Laboratory assessments:** These values should include: hematological test (hemoglobin, hematocrit, red blood cell count, platelet count, WBC and differential count [ANC, lymphocytes, monocytes, eosinophils and basophils, and other cells]); coagulation (INR, PTT (or aPTT)); chemistry panel (serum or plasma): sodium, potassium, chloride, glucose, BUN or urea, creatinine, total protein, albumin, phosphate, calcium, total bilirubin (if total bilirubin is 2xULN, also direct bilirubin), AST, ALT, ALP, urate and LDH; fasting lipid panel: cholesterol, LDL cholesterol, HDL cholesterol, and triglycerides (after ≥ 8 hours of fasting); urinalysis, including dipstick (pH, specific gravity, glucose, protein, ketones, and blood) and microscopic examination (sediment, RBCs, WBCs, casts, crystals, epithelial cells, and bacteria), FSH and estradiol. Baseline (Day 1, prior to initiation of study treatment) laboratory assessments are not required if the screening assessments were performed at within 14 days prior to initiation of study treatment.

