1.4 Study design

This is a multicenter, international, open-label, two-arms, one stage, phase II, window of opportunity, clinical trial aiming to assess changes in tumor cell proliferation as measured by Ki67 expression between baseline and post-treatment (day 15) tumor biopsy samples by central assessment in premenopausal women with ER[+]/HER2[-] & Ki67 $\geq 10\%$ early breast cancer (EBC).

Note: if post-treatment surgery or biopsy cannot be performed within + 1 day from last day of treatment (that is, on day 15 or the day after), treatment will be extended to 16 days and patients will be able to have surgery or biopsy the following day (be it D15 + 2 days).

After signing informed consent form (ICF) and confirmed eligibility, patients will be randomly assigned in a 1:1 ratio to receive either giredestrant (GDC-9545) 30 mg orally (PO) once a day (QD) or tamoxifen 20 mg PO QD as a single agent. 92 patients are expected to be enrolled in the study and treated for a total of 15 days.

[figure not shown]

Figure 1. EMPRESS study design. Abbreviations: d: days; ER: Estrogen receptor; PgR: Progesterone receptor; PO: orally; QD: daily; R: randomization.

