1.5 Study Schedule

The study will consist of a screening period of up to 28-day, a window-of-opportunity 15-day treatment phase, an End of Treatment visit (EoT) (+ 1 day after the final dose of study treatment) and an End of Study (EoS) visit (28 days \pm 3 days after the final dose of study treatment).

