1.5.2 Treatment Phase and End of Treatment visit

The treatment phase is defined as the time between the study entry and the last dose of study treatment received within this trial. After confirming eligibility through the screening process, patients will be scheduled for visit day 1 (D1) of treatment within 48 h after randomization.

In this first visit, medical history, including clinically significant diseases, surgeries, cancer history, and reproductive status will be recorded at baseline. In addition, all medications (e.g., prescription drugs, over-the-counter drugs, vaccines, herbal or homeopathic remedies, nutritional supplements) used by the patient within 7 days prior to initiation of study treatment will be recorded. Also, in this first visit D1, patients will be given the first dose of treatment and will be instructed how to take giredestrant or tamoxifen orally, daily at their homes during the following 14 days D2 to D15 (to finalize a total of 15 days of treatment).

To assess patient compliance with self-administration of study medication, site study staff will provide patients with detailed instructions and training for the handling and administration of study drugs. Patients will receive and should be instructed to complete a medication diary to record all relevant information during those days.

A second biopsy will be collected at the EoT (on day 15 or day 15 + 1), after last dose of study treatment is taken by the patient in the EoT visit. If a fresh post-treatment biopsy cannot be obtained within + 1 day from last day of treatment, treatment will be extended to 16 days and patients will be able to have surgery or biopsy the following day (be it D15 + 2 days).

If a mandatory procedure described in the protocol falls on a bank holiday and/or weekend, this procedure should be performed on the day before or after the holiday (i.e. within a period of ± 2 working days), with the exception of the post-treatment surgery or biopsy that must be performed on the last day of treatment or 1 day after last day of treatment.

All patients will be closely monitored for safety and tolerability during study treatment. Patients should be assessed for toxicity prior to any study treatment administration; dosing will occur only if the clinical assessment and local laboratory test values are acceptable.

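### The SAP's TEAE window stops at the last dose, and its partial-date rule ignores the first-dose date, so TEAE counts will be wrong if the rules are followed as written

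*SAP*

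**What the plan says.** **TEAE definition.** SAP 4.5.2: "Adverse events starting or worsening during treatment phase will be considered as TEAEs". It adds no days after dosing. The protocol does not define the term.

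**Treatment phase.** SAP 1.5.2, in the same words as protocol 3.3.2: "The treatment phase is defined as the time between the study entry and the last dose of study treatment received within this trial". Study entry is not defined. SAP 1.5 also speaks of "a window-of-opportunity 15-day treatment phase", and under SAP 1.4, if the post-treatment sample cannot be taken in time, "treatment will be extended to 16 days".

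**AE collection.** Protocol Appendix 1, footnote 9: "After initiation of study drug, all adverse events will be reported until 28 days (EoS) after the final dose of study treatment". The safety follow-up paragraph of the protocol synopsis gives the following of toxicity as a purpose of this period.

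**Incomplete dates.** SAP 4.5.2 sets a missing day to the 15th. For the other case the rule reads "Day 1 and month July if day and month are missing". Neither rule refers to the first dose. An AE that cannot be allocated counts as a TEAE.

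**Where TEAEs are used.** SAP 4.5.2 tabulates TEAEs and grade 3 or higher TEAEs. SAP 2.5 adds related TEAEs and TEAEs leading to dose change, discontinuation or death.

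**The concern.** The protocol follows patients for 28 days after the last dose partly to detect toxicity, yet no TEAE rule reaches into those days. The edge of the window also matters. After Day 1, the next scheduled laboratory tests and ECG are at the EoT visit, which may fall on the day after the last dose. An abnormality first dated at such a visit starts after the last dose and is not a TEAE.

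The date rule raises a separate problem. A window of 15 or 16 days is short against a calendar month, so a fixed mid-month date will often miss it. AE duration is computed only from complete dates, so TEAE allocation is the main visible use of an imputed onset date.

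At stake are the TEAE rows, above all the grade 3 or higher row, which has no all-AE counterpart in the SAP 4.5.2 list. With 46 patients per arm, one patient is 1/46 = 2.2 percentage points, so a few misplaced events show.

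**Working it through.** The documents give no figure for the TEAE window, so there is none to reproduce.

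**1. Days outside the window**

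Inputs: 15 treatment days (16 if extended); AE reporting to 28 days after the last dose, with the visit allowed 3 days either way.

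Share outside = follow-up days / (treatment days + follow-up days)

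- Nominal: 28 / (15 + 28) = 28/43 = 65%
- Lowest: 25 / (16 + 25) = 61%
- Highest: 31 / (15 + 31) = 67%

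**2. Where the window opens**

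Since study entry is undefined, three readings were carried through.

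- First dose: the reading that fits the 15-day description.
- Randomization: up to 2 days before first dose, because "patients will be scheduled for visit day 1 (D1) of treatment within 48 h after randomization".
- Start of screening: up to 28 days before first dose, because "The study will consist of a screening period of up to 28-day".

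**3. Missing day set to the 15th**

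Every first-dose date from 2023 to 2026 (1,461 dates) was combined with every treatment day. This gives 1,461 × 15 = 21,915 on-treatment onsets, or 1,461 × 16 = 23,376 if extended. Each onset was moved to the 15th of its own month and compared with the window. Start dates and onset days are taken as uniform.

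| Window opens | Dated before window (15-day course) | Dated after last dose (15-day course) | Lost, 15-day course | Lost, 16-day course |
|---|---|---|---|---|
| First dose | 6,078 | 5,040 | 11,118/21,915 = 51% | 11,146/23,376 = 48% |
| 2 days earlier | 4,672 | 5,040 | 9,712/21,915 = 44% | 9,712/23,376 = 42% |
| 28 days earlier | 0 | 5,040 | 5,040/21,915 = 23% | 5,040/23,376 = 22% |

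Two examples show how far this depends on the start date. With first dose on 1 March 2024 and last dose on 15 March, none of the 15 onset days is lost. With first dose on 20 March and last dose on 3 April, March onsets become 15 March, before first dose and before any randomization up to 2 days earlier. April onsets become 15 April, after the last dose. All 15 onset days are lost under the first two readings.

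The rule also works in the other direction. Of 1,461 × 28 = 40,908 follow-up onsets with a missing day, 6,078 to 6,106 (15%) are moved into the window.

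**4. Day and month missing, set to 1 July**

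Over the three readings and both course lengths, the share of on-treatment events placed outside the window runs from 20,560/23,376 = 88% (opening 28 days earlier, 16-day course) to 21,015/21,915 = 96% (opening at first dose, 15-day course).

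**5. Would a longer window be enough?**

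No. With a window from first dose to 28 days after the last dose and the 15th-of-month rule kept, 6,078/21,915 = 28% of day-missing on-treatment events (6,106/23,376 = 26% for 16 days) are still dated before first dose. If an onset compatible with the first-dose month takes the first-dose date, and a later month takes its first day, the loss is 0%.

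**The case against.** The strongest reply is that little is lost from the report as a whole. SAP 4.5.2 also tabulates all AEs, AESIs, SAEs, related AEs and related SAEs, and none of these is limited to the treatment phase. The SOC/PT tables in SAP 4.5 and 4.5.2 are AE-based. The secondary endpoint is stated in terms of AEs, and SAP 2.5 grades them by CTCAE. This stands. A reader might infer that the trial will miss late thromboembolic or hepatic events of special interest; the documents do not support that.

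Other parts of the reply also stand:

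- **Percentages.** The 65% must not be read as the share of AEs lost, nor the 51% as the share of TEAEs lost. The first counts days. The second applies only to on-treatment AEs with a missing day, and only if the window opens at first dose.
- **Direction.** Because some follow-up events are moved in, the bias from imputation is not purely downward.
- **Pre-dose events.** It is tempting to say that they inflate the TEAE count. Appendix 1 begins the treatment period at Day 1, and footnote 9 limits pre-dose reporting to SAEs caused by protocol procedures, so this part is nearly empty. Protocol 7.2 collects AEs from the first mandated procedure; the two places should be reconciled.
- **Fallback.** It is not dead letter. An onset with no year has no imputation rule, cannot be allocated, and becomes a TEAE. It does not help when only the day, or the day and month, are missing, because imputation then supplies a date.
- **Window length.** Surgery may take place at the end of treatment, so the follow-up can be a post-operative period. A TEAE window limited to treatment, beside unrestricted AE tables, is a defensible choice. The plan does not present it as one, and leaves the start of the window undefined.

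What the reply does not answer is the date rule, which is wrong for any window this short.

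**Conclusion.** The point holds for the TEAE outputs only. As written, SAP 4.5.2 excludes AEs with onset in the follow-up, including one first dated at an EoT visit the day after the last dose, from the TEAE and grade 3 or higher TEAE rows and the TEAE summaries of SAP 2.5. Independently, its date rule takes on-treatment events out of the window: 51%, 44% or 23% of day-missing events according to where the window opens, and 88% to 96% under the 1 July rule.

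These shares assume uniform start and onset dates. The number of incomplete dates is not given and may be small, so the effect on actual counts cannot be stated.

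This is a should-fix. A reader might rank it higher, but the Ki67 primary analysis does not depend on it, safety is descriptive, no decision rule uses TEAEs, and every event remains in at least one output.

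**What to change.** In SAP 4.5.2:

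1. Define a TEAE as an AE that starts or worsens from the first dose until 28 (+3) days after the last dose. This also removes the dependence on study entry.
2. Replace the fixed dates. If the known parts of an onset date are compatible with the first-dose month (or year), impute the first-dose date; otherwise impute the first day of the known month or year. Classify an AE as non-TEAE only if its known date parts prove onset outside the window.

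Both changes are needed, as step 5 of the working shows. The cost is a few sentences and one derivation; all the data are already collected. There are two downsides. Post-surgery events enter the TEAE tables and must be separated by the recorded causality assessment, or a row limited to the dosing period can be kept alongside. Some pre-dose or late events with incomplete dates will also be counted as TEAEs, which errs on the cautious side.
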